4.1.4 Safety and tolerability analysis

AEs incidence will be compared between the trial arms using Pearson's chi-squared test. In case of significant changes, a relative risk will be calculated (with 95% CI).

A tolerability level for every group will be calculated based on the AEs incidence and nature (in accordance with Section 2.3 of this Plan).

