3.1 Trial objective

The objective of this trial is evaluation of non-inferiority of the therapeutic efficacy and safety of the study drug Angal S, topical spray [menthol], containing 0.5 mg of lidocaine hydrochloride and 2 mg of chlorhexidine digluconate per ml (Sandoz d.d., Slovenia), when compared to ANTI-ANGIN® FORMULA, topical metered spray, containing 0.12 mg of tetracaine hydrochloride and 0.24 mg of chlorhexidine bigluconate per dose (OOO Valeant, Russia), in treatment of patients with uncomplicated acute infectious and inflammatory diseases of the pharynx accompanied by a sore throat.

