9.1.4 Safety parameters analysis

A descriptive part of the safety analysis will include an evaluation of incidences and two-sided CI 95% for the following parameters in every trial group:

- AEs: the incidence in total and for separate categories (according to MedDRA), for the trial and by groups;
- SAEs: the incidence in total and for separate categories (according to MedDRA), for the trial and by groups;
- Incidence of clinically significant changes of the physical examination results by visits and groups;
- Incidence of clinically significant changes of the laboratory results by visits and groups;
- Incidence of clinically significant changes of the vital signs (body temperature, BP, pulse rate, HR) by visits and groups;
- Incidence of clinically significant changes of the ECG parameters by visits and groups;
- Global tolerance evaluation during the trial by the Investigator and patient.

The Fisher's exact test will be used to compare incidences between the groups, and chi-square will be used to compare the global therapy tolerability by the Investigator and patient. The McNemar's test will be used to evaluate for the dynamic changes during the trial (before—after) for all the repeatedly evaluated incidences in every group.

In addition to the incidence, all the quantitative safety parameters will be presented in a table form (laboratory results, vital signs, ECG) by visits and groups. The difference will be evaluated using 2-way-ANOVA (group and visit numbers will serve as the relevant factors). The post-hoc criteria will be used in case of significant difference.

Safety analysis will be performed on the safety population.

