9.2 Planned number of subjects

A statistical objective of the trial will be a prove of a non-inferior therapeutic efficacy and safety of the study drug Angal S comparing to the drug ANTI-ANGIN® FORMULA in the treatment of acute infectious and inflammatory diseases of the pharynx. Justification of a non-inferiority margin is based on the results of a placebo-controlled trial of pastilles with chlorhexidine and lidocaine conducted by [Kris De Ceulaer. A summary of a clinical trial proves that chlorhexidine/lidocaine lozenges are effective and safe. 11-8-2015].

This trial demonstrated absence of a sore throat (a TSS subscale) 3 days after the therapy initiation, on Day 4, in 37.5% patients in the trial arm and 63.1% patients in the placebo arm.

Table 2. Answers distribution results regarding questions on a sore throat at baseline and Day 4

	Baselii	ne visit	Ι)4
N	Product N=106	Placebo N=103	Product N=106	Placebo N=103
Sore throat				
Unknown	0	0	2 (N=104)	0
Absent	0 (0%)	0 (0%)	65 (62.5%)	38 (36.9%)
Mild	3 (2.8%)	3 (2.9%)	27 (26.0%)	45 (43.7%)
Moderate	77 (72.6%)	75 (72.8%)	11 (10.6%)	19 (18.4%)
Severe	26 (24.5%)	25 (24.3%)	1 (1.0%)	1 (1.0%)
p	1.0000		0.0	0016

Therefore, a lower limit of CI boundary may be calculated for the difference in sore throat presence after 3 days of therapy, taking into account 104 participants and 103 patients.

In view of the considered nosology and absence of significant factors requiring a conservative approach for determination of the

non-inferiority margin, for this purpose we can use a two-sided CI 90%. To calculate a two-sided CI 90%, a method described by Newcombe, Robert G. was used "Interval Estimation for the Difference Between Independent Proportions: Comparison of Eleven Methods," Statistics in Medicine, 17, 873-890 (1998). CI 90% will amount to 14.56–36.66%, i.e., the lower limit will correspond to one-sided CI 95%. Therefore, a margin of 14.5% is considered to be justified.

NCSS 8.0 Two Proportions Report

Dataset Untitled

Zero Adjustment Method: None

Note: Exact tests and c.i.'s were not run because total count > 50 (specified under 'Reports' tab).

Table Section

				N1	N2	M1	M2	N
A	В	\mathbf{C}	D	(A+C)	(B+D)	(A+B)	(C+D)	(N1+N2)
65	39	38	65	103	104	104	103	207

Confidence Intervals of Difference (P1-P2)

Interval	Estimated	Confidence	Confidence
Method	Value	Limit	Limit
Chi-Square (Pearson)	0.2561	0.1456	0.3666

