This trial has been designed and conducted to evaluate non-inferiority of the therapeutic efficacy and safety of the study drug Angal S, topical spray [menthol] containing 0.5 mg of lidocaine hydrochloride and 2 mg of chlorhexidine digluconate per ml (Sandoz d.d., Slovenia), when compared to ANTI-ANGIN® FORMULA, topical metered spray giving 0.12 mg of tetracaine hydrochloride and 0.24 mg of chlorhexidine bigluconate per dose (OOO Valeant, Russia) in the treatment of patients with uncomplicated acute infectious and inflammatory diseases of the pharynx accompanied by a sore throat. The objective of this Phase III trial is to demonstrate the non-inferior therapeutic efficacy of the study drug as compared to the reference product.

This Statistical Analysis Plan was developed in accordance with the following documents:

- Guidelines for examination of medicinal products, Vol. 1. Federal State Budgetary Institution Scientific Center for Expert Evaluation of Medicinal Products under the Ministry of Health of the Russian Federation (eds. A.N. Mironov). Moscow: Grif and K, 2013.
- ICH harmonized tripartite guideline. Statistical principles for clinical trials (E9). Current Step 4 version dated 5 February 1998.
- GCP rules of the Eurasian Economic Union (a draft).

The objective of this Statistical Analysis Plan is more detailed, compared to Section 9 of the trial protocol, description of the main principles of the protocol-based statistical analysis, description of the primary and secondary endpoints analysis methods, as well as other data obtained during the trial.

This Plan stipulates for consistence of the scheduled and conducted statistical analysis to the trial protocol, including definition of the analysis data sets, transformations and calculations for the endpoints, observations quantity needed, etc. No changes in this Statistical Analysis Plan compared to the trial protocol are envisaged.

2. Trial endpoints

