3.10 Significance level

All statistical analyses in this trial will be conducted at 95% significance level (a threshold p value for confirmation of statistical significance is below 0.05), except for the primary endpoint where a one-sided statistical criterion will be used with 95% significance level (a threshold p value is below 0.05). The two-sided statistical criteria will be used for all other parameters.

For the primary endpoint evaluation, 90% CI will be calculated for the proportions difference with further evaluation of its lower boundary limit.

4 Analysis plan

For non-inferiority confirmation, a two-sided 90% CI will be calculated for the proportion difference of the primary efficacy parameters (no pain after 3 days of therapy on Day 4 according to TSS) with further evaluation of its lower boundary limit.

A non-inferiority conclusion will be made relating to the primary parameter only which will confirm the claimed efficacy. Secondary variables (including secondary efficacy and safety parameters) will be used for the research interest. Correction for multiple comparisons is not envisaged due to the trial arms number.

Descriptive statistics will include data for all randomized patients. Descriptive statistics parameters to be calculated for the quantitative variables are listed below:

- Quantity of observations (n);
- Arithmetic mean (M);
- Standard deviation (SD);
- 95% confidence interval for the mean (95% CI);
- Minimal value (min.);
- Maximal value (max.);
- Median (Me);
- Interquartile range (IQR).

For the variables presented as qualitative and serial parameters, the absolute (n) and relative (%) incidences will be calculated for every category, as well as 95% CI (unless otherwise specified).

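### The AE relative risk is calculated only after a significant test, so no between-arm safety contrast is planned otherwise, and the stated non-inferior safety objective has no margin and conflicts with SAP section 4

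*SAP*

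**What the plan says.** **Reporting rule.** SAP 4.1.4 states that "AEs incidence will be compared between the trial arms using Pearson's chi-squared test", followed by "In case of significant changes, a relative risk will be calculated (with 95% CI"). SAP 3.10 sets the cut-off: "a threshold p value for confirmation of statistical significance is below 0.05", and, outside the primary endpoint, "The two-sided statistical criteria will be used for all other parameters".

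**What is reported in any case.** Protocol 9.1.4 gives AE and SAE incidences in each group with two-sided 95% CIs. It also says "The Fisher's exact test will be used to compare incidences between the groups", so the two documents name different tests. It names no between-arm AE estimate. The shell of SAP Table 23 has n/N (%) for each arm and a p column, with no column for a contrast or its CI.

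**Objective.** Protocol 3.1 describes the objective as "evaluation of non-inferiority of the therapeutic efficacy and safety of the study drug Angal S". Protocol 9.2 makes it statistical: "A statistical objective of the trial will be a prove of a non-inferior therapeutic efficacy and safety". SAP 1 says the trial was set up to "evaluate non-inferiority of the therapeutic efficacy and safety of the study drug Angal S". The synopsis repeats this under trial objective and statistical analysis. Protocol 3.2 is narrower: the primary goal is non-inferior efficacy, and the secondary goals are to evaluate safety and to compare AE rates between the arms.

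**Limit on the conclusion.** The opening of SAP section 4 restricts the non-inferiority conclusion to the primary efficacy parameter and treats safety variables as being of research interest.

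**The concern.** There are two linked problems.

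First, the contrast depends on the test result. If the two sprays have similar AE rates, the test will usually be non-significant. The relative risk and its interval are then not produced, and the interval is what would show how large an excess the data still allow. The p-value does not show this, and two separate per-arm intervals are not an interval for the difference. SAP 4.1.2 handles efficacy the other way: the difference in proportions and its CI are given whatever the result.

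Second, several passages promise non-inferior safety, and the design has no means of testing it. The 14.5% margin and the formal hypotheses in Protocol 9.2 and SAP 3.9 concern the primary efficacy endpoint only. At stake is how informative the safety comparison in the report will be, and whether the objective matches the analysis. The efficacy conclusion is not at stake.

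**Working it through.** The documents state no AE rate, safety margin or safety power, so there is no figure of theirs to reproduce. The counts and rates below are assumptions, used to show what the rule would leave out.

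**Inputs.** n = 140 per arm (Protocol 9.2, number randomized); two-sided 0.05 (SAP 3.10); Pearson chi-squared without continuity correction (test from SAP 4.1.4; leaving out the correction is my choice). Counts are patients with at least one AE.

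**Example, 8 v 3 patients (assumed).**
- Rates: 8/140 = 5.71% and 3/140 = 2.14%.
- Test: chi-squared = 2.37, p = 0.12. Not significant, so no relative risk is calculated.
- Risk difference: 5.71 - 2.14 = +3.57 points. SE = sqrt(0.0571 x 0.9429/140 + 0.0214 x 0.9786/140) = 0.0231. Wald 95% CI: 3.57 ± 1.96 x 2.31 = -1.0 to +8.1 points. The Newcombe method, which the plan names for efficacy, gives -1.3 to +8.9.
- Relative risk: 8/3 = 2.67. SE of log RR = sqrt(1/8 - 1/140 + 1/3 - 1/140) = 0.666. 95% CI: exp(0.981 ± 1.96 x 0.666) = 0.72 to 9.84.

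**Largest excess that still gives p ≥ 0.05, and the interval if the counts are equal** (same formulas):

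| Assumed comparator rate | Comparator count | Largest non-significant count | p | RR (95% CI) not reported | 95% CI if counts are equal (RR 1.0) |
|---|---|---|---|---|---|
| 2% | 3 | 9 | 0.077 | 3.00 (0.83 to 10.85) | 0.21 to 4.87 |
| 5% | 7 | 16 | 0.050* | 2.29 (0.97 to 5.38) | 0.36 to 2.78 |
| 10% | 14 | 25 | 0.058 | 1.79 (0.97 to 3.29) | 0.50 to 2.02 |
| 20% | 28 | 42 | 0.053 | 1.50 (0.99 to 2.28) | 0.63 to 1.60 |

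*0.0501, just above the threshold.

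**How often the relative risk would be calculated** (simulation, 40,000 trials, 140 per arm). If the true relative risk is 1, it appears in about 5% of trials. If it is 2, it appears in about 15%, 35%, 66% and 96% of trials at comparator rates of 2%, 5%, 10% and 20%. At assumed rates of 5% or less, even a true doubling would usually leave no contrast in the report.

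**Objective against rule.** Protocol 3.1 and 9.2, SAP 1 and the synopsis attach non-inferiority to safety. SAP section 4 allows that conclusion for the primary efficacy parameter alone, and neither document sets a margin or hypothesis for safety. Both positions cannot stand.

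**The case against.** The strongest reply is that the plan never claims what a reader might infer from it. It is tempting to say that a non-significant AE test will be presented as no difference, or as non-inferior safety. No passage says so, and SAP section 4 points the other way by keeping the non-inferiority conclusion to efficacy. Protocol 3.2 and the formal hypotheses do the same. SAP 1 itself goes on to give non-inferior therapeutic efficacy as the objective of the Phase III trial. On this view the references to safety are loose wording on which no decision rule depends. That stands as far as it goes. It makes the objective a conflict to reconcile, and it does not supply the missing contrast.

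A second tempting reading is that the AE estimates and their precision are absent altogether. They are not. Per-arm incidences with 95% CIs are reported whatever the p-value, and a reader could derive a risk difference or relative risk from the counts. Only the planned between-arm contrast and its interval are missing. For the same reason, the worry that an estimate shown only after significance will be inflated has limited force: the per-arm rates are not selected on significance.

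It is also true that 8 v 3 is a chosen example and that the documents give no reference value for an important excess. The example shows a mechanism and does not predict a result.

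**Conclusion.** The point holds for the between-arm contrast. The relative risk and its CI are conditional on significance, nothing else in either document supplies a contrast, and the rule serves poorly the stated goal of comparing AE rates. The non-significant result is the likely one if the arms have similar AE rates, with about 95% of trials non-significant under equality.

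The size rests on 140 analysed per arm and on assumed AE rates. Over comparator rates of 2% to 20%, the largest observed relative risk that could go unreported runs from 3.0 down to 1.5, with upper limits from about 10.9 down to 2.3.

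Separately, the non-inferior safety wording conflicts with SAP section 4 and has no margin behind it. The documents do not support the further inference that the sponsor plans to read non-significance as safety equivalence. This is a reporting and wording defect worth correcting. It does not touch the primary conclusion.

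**What to change.** 1. In SAP 4.1.4, remove the significance condition. Report the risk difference and relative risk, each with a two-sided 95% CI, for patients with any AE, with related AEs and with SAEs, whatever the p-value. Name a score or exact method for sparse counts, since log-scale Wald limits are unreliable there and undefined when an arm has no events.
2. Add the matching columns to SAP Table 23, with rows for these three summaries.
3. In the synopsis (trial objective and statistical analysis), Protocol 3.1 and 9.2, and SAP 1, limit non-inferiority to efficacy and describe safety as a comparative estimate, in line with SAP section 4. The clinical trials program text in Protocol section 2 has the same wording and needs the same edit.
4. While editing, reconcile the AE test, which is Fisher's exact in Protocol 9.1.4 and Pearson chi-squared in SAP 4.1.4. Once the contrast is unconditional, the choice affects only the p-value.

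The cost is a few table columns and a wording amendment. No extra patients or data are needed, and the primary analysis is unchanged.

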3.2 Trial goals

Primary goal:

• Evaluation of non-inferiority of the therapeutic efficacy of Angal S, topical spray [menthol], containing 0.5 mg of lidocaine hydrochloride and 2 mg of chlorhexidine digluconate per 1 ml (Sandoz d.d., Slovenia); one dose includes 3 to 5 consecutive presses on the actuator button, six to ten times per day, for 4 days or until full recovery (whichever occurs first during 4 days of therapy), compared to ANTI-ANGIN® FORMULA, topical metered spray, containing 0.12 mg of tetracaine hydrochloride and 0.24 mg of chlorhexidine bigluconate per dose (OOO Valeant, Russia); one dose includes 1 to 2 consecutive presses on the actuator button, up to 6 times per day, for 5 days or until full recovery (whichever occurs first during 5 days of therapy), in patients with uncomplicated, acute, infectious and inflammatory diseases of the pharynx accompanied by a sore throat.

Secondary goals:

• Evaluation of safety of Angal S, topical spray [menthol], containing 0.5 mg of lidocaine hydrochloride and 2 mg of chlorhexidine digluconate per 1 ml (Sandoz d.d., Slovenia); one dose includes 3 to 5 consecutive presses on the actuator button, six to ten times per day, for 4 days or until full recovery (whichever occurs first during 4 days of therapy), compared to ANTI-ANGIN® FORMULA, topical metered spray, containing 0.12 mg of tetracaine hydrochloride and 0.24 mg of chlorhexidine bigluconate per dose (OOO Valeant, Russia); one dose includes 1 to 2 consecutive presses on the actuator button, up to 6 times per day, for 5 days or until full recovery (whichever occurs

first during 5 days of therapy), in patients with uncomplicated, acute, infectious and inflammatory diseases of the pharynx accompanied by a sore throat.

- Evaluation of adverse events (AEs) in the trial arms.
- The AEs rate comparison between the trial arms.

Protocol No. TE 003 ANG LSP

4 Trial design

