2.3 Evaluation of the study drug safety and tolerance

Safety of the trial therapy is evaluated based on the systemic parameters (systolic and diastolic blood pressure, breathing rate, heart rate, body temperature, ECG), laboratory tests results, frequency of adverse events (AEs) and serious adverse events (SAEs). AEs nature and incidence (allergic reactions, burning sensation, discomfort) at the administration site will be evaluated throughout the trial. Global evaluation of treatment tolerability will be made by the patient and the physician according to the following scale:

Scores	Evaluation
0	Poor

1	Satisfactory
2	Good
3	Excellent

Evaluation of the study drug tolerability by the patient and the physician (points/scores) should be specified in the eCRF at Visits 2 or 3 (where applicable).

3 Main provisions for analysis

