4.1.2 Primary endpoint

The primary endpoint of the trial (absence of the sore throat after 3 days of therapy on Day 4) will be presented as the difference between the proportions for each arm. The group comparison will be carried out using the Fisher's exact test (one-sided test, in connection with the null hypothesis of non-inferiority). For the proportion difference, the 90% confidence interval (CI) will be calculated according to the procedure described in Newcombe, Robert G. "Interval Estimation for the Difference Between Independent Proportions: Comparison of Eleven Methods," Statistics in Medicine, 17, 873-890 (1998).

Thus, the non-inferiority will be confirmed if the limit of the two-sided 90% confidence interval for the difference in the proportions will be 14.5% or lower.

A primary endpoint analysis will be conducted both for the ITT (main analysis) and PP populations (additional analysis).

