Description	Serious	Non-serious	Serious	Non-serious	Serious	Non-serious	Serious	Non-serious	Serious +
	Scrious	1voii-scrious	Scrious	1 voii-scrious	Scrious	1 voii-serious	Scrious	14011-SCI IOUS	non-serious
				Organ sys	tem				
				Organ sys	tem				
_							•		

Table 22. Registered adverse events occurred after initiation of the reference therapy

	Milo	d AEs	Moder	ate AEs	Seve	re AEs	To	otal	Total
Description	Serious	Non-serious	Serious	Non-serious	Serious	Non-serious	Serious	Non-serious	Serious +
	Serious	Tion serious	5 6110 415	T (OII DOTTOUS	5411045	T (OII DUTTO GO	Serrous	1 (011 50110 45	non-serious
				Organ sys	tem				
	Organ system								

Table 23. AEs frequency by the nosological groups

Nosological group	Arm	Arm	p
Nosological group 1	n/N (%)	n/N (%)	
Nosology 1	n/N (%)	n/N (%)	
Nosology 2	n/N (%)	n/N (%)	
Nosology 3	n/N (%)	n/N (%)	
Nosological group 1	n/N (%)	n/N (%)	
Nosology 1	n/N (%)	n/N (%)	
Nosology 2	n/N (%)	n/N (%)	

Nosology 3	n/N (%)	n/N (%)	
Nosology 3	II/IN (/0)	11/1N (/0)	

Table 24. Compliance evaluation

Arm	Parameter	Compliance
	n	
	M	
	SD	
	95% CI	
	Min.	
	Max.	
	Me	
	IQR	
	n	
	M	
	SD	
	95% CI	
	Min.	
	Max.	
	Me	
	IQR	
	p	

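### SAP 4.1.4 plans a between-arm AE estimate only after a significant test, so a non-significant AE comparison has no planned interval for the difference

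*SAP*

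**What the plan says.** - SAP 4.1.4 tests AE incidence between arms with Pearson's chi-squared test and adds: "In case of significant changes, a relative risk will be calculated (with 95% CI"). SAP 3.10 sets two-sided testing at 0.05 for everything except the primary endpoint.
- Protocol 9.1.4 plans an "evaluation of incidences and two-sided CI 95% for the following parameters in every trial group", and names Fisher's exact test for comparing incidences between groups. It names no effect measure.
- SAP section 4 gives n, % and 95% CI per category, and SAP 4.1.1 presents these for each group separately.
- SAP Table 23, "AEs frequency by the nosological groups", has n/N (%) for each arm and a p column.
- SAP 2.3 singles out local reactions: "AEs nature and incidence (allergic reactions, burning sensation, discomfort) at the administration site will be evaluated throughout the trial". It gives them no separate between-arm analysis.
- Protocol 3.2 lists as a secondary goal: "The AEs rate comparison between the trial arms". Protocol 3.1 says: "The objective of this trial is evaluation of non-inferiority of the therapeutic efficacy and safety of the study drug Angal S".
- SAP section 4 limits what will be concluded: "A non-inferiority conclusion will be made relating to the primary parameter only". It describes safety variables as of research interest.

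**The concern.** A significance test is a poor gate for reporting a safety estimate. The question about AEs is how large a difference the data still allow. That question is most open when the test is not significant, which is when the plan produces no between-arm interval. A p value above 0.05 is then easily read as similar safety.

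The gate also distorts the estimates that do get through. If a relative risk is shown only when p<0.05, the values shown come from the upper part of its sampling distribution and overstate the true ratio on average.

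At stake is how well the report can meet its own goal of comparing AE rates. That includes local reactions, which are relevant for two throat sprays: Protocol 2.1.2 lists burning of the oral mucosa for the comparator, and Protocol 2.1.1 lists a burning sensation on the tongue for Angal S.

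**Working it through.** The plan states no AE figure, so there is nothing to reproduce. The check has three parts.

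**1. Is an ungated between-arm AE estimate planned anywhere?**

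| Place | AE output | Between-arm estimate with CI? |
|---|---|---|
| Protocol 9.1.4 | incidence and 95% CI per arm; Fisher test | no |
| SAP 4 and 4.1.1 | n, %, 95% CI, each group separately | no |
| SAP 4.1.4 | Pearson test; relative risk with 95% CI | only if significant |
| SAP Table 23 | n/N (%) per arm; p | no |

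No such estimate is planned.

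**2. What goes unreported?** Inputs: 140 per arm (Protocol 9.2) and two-sided 0.05 (SAP 3.10). The AE counts are assumptions, because the documents give no expected AE rates for this trial.

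Pearson, uncorrected: X² = d² / [p̄(1-p̄)·2/n], with d = p₁-p₂ and p̄ the pooled proportion.

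Newcombe interval, with Wilson limits (l, u) for each arm:
- lower = d - √[(p₁-l₁)² + (u₂-p₂)²]
- upper = d + √[(u₁-p₁)² + (p₂-l₂)²]

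For 11 v 4 (Angal S v comparator):
- p₁ = 11/140 = 0.0786, Wilson 0.0444 to 0.1352
- p₂ = 4/140 = 0.0286, Wilson 0.0112 to 0.0712
- d = 0.0500; p̄ = 15/280; X² = 3.45; p = 0.063
- lower = 0.0500 - √(0.0342² + 0.0426²) = -0.005
- upper = 0.0500 + √(0.0566² + 0.0174²) = 0.109

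The same steps for other counts:

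| Counts | Pearson p | Relative risk planned? | Difference, points (Newcombe 95% CI) |
|---|---|---|---|
| 11 v 4 | 0.063 | no | 5.0 (-0.5 to 10.9) |
| 25 v 14 | 0.058 | no | 7.9 (-0.3 to 16.1) |
| 42 v 28 | 0.053 | no | 10.0 (-0.2 to 19.9) |
| 4 v 4 | 1.0 | no | 0 (-4.6 to 4.6) |
| 14 v 14 | 1.0 | no | 0 (-7.3 to 7.3) |

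In each of the first three rows, one more Angal S patient takes Pearson's p below 0.05 (12 v 4: 0.039; 26 v 14: 0.040; 43 v 28: 0.039). A single patient then decides whether any estimate appears.

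**3. How far does the gate inflate the relative risk?** I enumerated all binomial outcomes at 140 per arm, kept those with Pearson p<0.05 and took the geometric mean relative risk, leaving out zero cells. True rates are assumed.

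| True rates | True RR | P(p<0.05) | Mean RR when shown | Factor |
|---|---|---|---|---|
| 20% v 12% | 1.67 | 0.45 | 2.18 | 1.31 |
| 15% v 10% | 1.50 | 0.24 | 2.34 | 1.56 |
| 10% v 5% | 2.00 | 0.35 | 3.48 | 1.74 |

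In these scenarios a real difference gets no between-arm estimate 55% to 76% of the time (1-0.45 and 1-0.24).

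**The case against.** The case for leaving the plan alone has real content.

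- *Uncertainty is not absent.* Each arm's AE incidence has a planned 95% CI, and a reader can derive the difference from n/N. This stands, but two separate intervals are not an interval for the difference, and the report is not planned to show one.
- *No decision depends on it.* There is no safety margin and no AE decision rule, and the non-inferiority conclusion is confined to the primary parameter. This stands and keeps the point small.
- *Table 23 is weak evidence.* It lacks a relative-risk column too, although SAP 4.1.4 plans that estimate. This is fair: the point rests on the wording of 4.1.4 and the absence of any other rule. The table shell only agrees with it.

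Three stronger readings are tempting, and the documents do not support them.

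- A reader might infer that the AE p value would be the only between-arm safety result. Protocol 9.1.4 also compares global tolerability, and SAP 4.1.5 compares vital signs, laboratory results and ECG changes. The gap is confined to AE incidence.
- A reader might infer that the rule will call for an undefined relative risk when the comparator has no events. At 4 v 0 of 140 Pearson gives p=0.044, but the protocol's Fisher test gives p=0.12 and triggers nothing. The documents disagree on the test, so this example holds only under the SAP's choice.
- A reader might infer that local reactions need their own composite. SAP 2.3 defines none. A composite that left out TSS symptoms would also drop difficulty swallowing, which is both a listed Angal S reaction (Protocol 2.1.1) and a TSS item.

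**Conclusion.** The concern holds as a reporting gap. The only planned between-arm estimate of AE incidence is conditional on significance, so a non-significant AE comparison has no planned interval for the difference.

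At 140 per arm and with assumed counts, non-significant results can leave upper limits of about 11 points (11 v 4) or 16 points (25 v 14) unreported. Relative risks that pass the gate are inflated by a factor of about 1.3 to 1.7 in the three assumed scenarios. The 10% v 5% case, at 1.74, is the most extreme of these and should not be quoted alone. The sizes depend on assumed AE rates and on Pearson's test; the gap itself depends on neither.

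It would go too far to infer that the trial's main conclusion is weakened. The SAP confines that conclusion to the primary parameter.

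**What to change.** In SAP 4.1.4, replace the conditional sentence with:

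> The risk difference (Angal S minus ANTI-ANGIN FORMULA) with Newcombe 95% CI will be reported whatever the p value, for total AEs and for every row of Table 23; a relative risk with 95% CI may also be given where both arms have events.

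Add a column to Table 23 for the difference and its CI. Covering every row matters, because a rule for selected rows only would remove the estimate now planned for a significant result in any other category. The local reactions named in SAP 2.3 are then covered through their own rows.

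The interval method is already in use for the primary endpoint (SAP 4.1.2: "For the proportion difference, the 90% confidence interval (CI) will be calculated according to the procedure" of Newcombe), at 90% there and 95% here.

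The cost is one sentence and one table column, using AEs already collected and MedDRA-coded. The downside is a somewhat larger table holding many descriptive intervals not adjusted for multiplicity. The report should say so, and should not present them as a second non-inferiority test.
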